11.3 Exploratory Endpoints

- OS, DOR, TTP.
 - Overall survival (OS) is defined as the number of months from the first dose of retifanlimab until death or end of follow-up (OS will be censored on the date the subject was last known to be alive for subjects without documentation of death at the time of analysis).
 - Duration of Response (DOR) is defined as the number of months from the first documentation of a response to date of disease progression.
 - Time to-progression (TTP) is defined as the number of months from the first dose of retifanlimab to the date of documented disease progression (PD or relapse from CR as assessed using RECIST 1.1 criteria). It differs from PFS in that it does not include death in the definition of an event. TTP will be censored at the date of the last scan for subjects without documentation of disease progression at the time of analysis.
 - Disease control rate (DCR) is defined as the proportion of subjects with complete response, partial response and stable disease
- Disease control rate, objective response rate, progression-free survival, and duration of response measured by iRECIST
- Immune subset analyses by IHC, next generation sequencing and gene expression profiling of tumor tissue
- Immune subset analyses in PBMCs including effector, helper, and regulatory T cells, NK cells, and macrophages
- Circulating cytokine analysis in patient sera
- Immune checkpoint analysis by IHC and gene expression profiling
- Tumor marker kinetics measured by change in serum CA19-9 concentrations from baseline

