11.2 Secondary Endpoints

The secondary endpoints are as follows:

- ORR is defined as the proportion of subjects with PR or CR according to RECIST 1.1. Subjects who discontinue due to toxicity or clinical progression prior to post-baseline tumor assessments will be considered as non-responders. Otherwise, subjects who discontinue or do not have any post-baseline scans for other reasons including withdrawal of consent or being lost to follow-up prior to C2D1 will be replaced and not included in the primary efficacy analysis.
- Progression-free survival (PFS) is defined as the number of months from the first
 dose of retifanlimab to radiographic disease progression (PD or relapse from CR
 as assessed using RECIST 1.1 criteria), documented clinical progression as
 assessed by the treating provider, or death due to any cause. PFS will be censored
 at the date of the last scan for subjects without documentation of disease
 progression at the time of analysis.
- Safety assessed by the following measures:
 - Number of patients who have grade 3 or above drug-related toxicities
 - Frequency of drug-related toxicity by grade
 - Retifanlimab-related infusion reactions
 - Immune-related AEs
 - Unacceptable toxicities
 - Vital signs: BP, pulse, temperature
 - Physical examination
 - Changes in ECG readings
 - Clinical hematology: complete blood count (CBC) with differential ANC,
 ALC, AEC, and platelet count
 - Clinical serum chemistry: sodium, potassium, chloride, bicarbonate, glucose, blood urea nitrogen (BUN), creatinine, lactate dehydrogenase (LDH), ALT, AST, alkaline phosphatase, lipase, bilirubin (total), total protein, albumin, calcium, magnesium and phosphate

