13.2 Data and Analysis Plan

Analysis of Primary Endpoint

The primary endpoint of the study will be disease control (DC) at four months using RECIST 1.1. DC is defined as complete response, partial response and stable disease at 4 months, per RECIST 1.1. Disease control rate (DCR) will be estimated as the proportion of patients who achieve DC at 4 months, along with 95% confidence interval

Analysis of Secondary Clinical Endpoint

The objective response rate defined as the proportion of response evaluable subjects who have a complete response (CR) or partial response (PR) using RECIST 1.1 criteria at any time during the study. The evaluable population includes all subjects who have completed at least one dose of retifanlimab and have received at least one follow-up scan or discontinue due to toxicity or clinical progression prior to post-baseline tumor assessments. Response rate will be reported with exact 95% confidence interval.

Progression-free Survival (PFS) is defined as the time from cycle 1, day 1 of retifanlimab until first documented local progression or death due to any cause. Disease progression will be assessed using RECIST (version 1.1) and/or documented clinical progression as assessed by the treating provider. Due to the expectation that some patients may experience delayed clinical responses to therapy, patients with disease progression by radiographic imaging or laboratory parameters during a 12-week evaluation period but without rapid clinical deterioration or significant change in performance status that requires additional immediate therapy may continue to receive treatment on study. Subjects that meet the above criteria and continue on study therapy must discontinue treatment upon documentation of disease progression on the second scan. The date of progression will be backdated to the time of first RECIST criteria progression. Tumor assessments will be made using RECIST 1.1 and immune RECIST (iRECIST). Individuals will be censored at the date of the last scan prior to initiation of an alternative therapy for PFS if no event occurs before the start of the alternative therapy.

PFS will be summarized descriptively using the Kaplan-Meier method. Analysis of PFS will be restricted to evaluable individuals who complete at least one dose of retifanlimab.

Analysis of Safety Endpoints

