The safety analysis will be performed in all subjects who receive at least one dose of study drug. A baseline measurement and at least 1 laboratory or other safety-related measurement obtained after at least 1 dose of study treatment may be required for inclusion in the analysis of a specific safety parameter (e.g., lab shifts from baseline). A complete list of all AE data will be provided along with an assessment of NCI CTCAE grade and relationship to study drug. The incidence of AEs will be tabulated by subgroups of interest (e.g. grade 3 or higher, organ class, relationship to study drug). For analyses at the individual level, the highest grade and relationship to study drug will be assumed if multiple events have occurred. Toxicity will be tabulated by type and grade and will be summarized with descriptive statistics. Other safety data will be assessed in terms of

physical examination, clinical chemistry, hematology, vital signs, and ECGs. Negative binomial regression and Cox proportional hazards models will be used to assess the rate of AE and time to first toxicity, respectively.

Exploratory Clinical Analysis

Overall survival is defined as the duration of time from start of study treatment to time of death. For subjects lost to follow-up or whose vital status is unknown, every effort will be made to determine the date such subjects were last known to be alive. Such efforts may include phone calls, certified mail, and the checking of public records. Subjects who are alive or lost to follow-up as of the data analysis cutoff date will be right-censored. The censoring date will be determined from the date the subject was last known to be alive.

OS will be summarized descriptively using the Kaplan-Meier method. Analysis of OS will be restricted to evaluable individuals who complete at least one dose of retifanlimab. Median event-free survival will be reported and the associated 95% confidence interval will be estimated.

DOR and TTP were defined in second 11.3.

Exploratory Biomarker Analysis

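### Section 11.3 names death as the difference between TTP and PFS, but TTP also leaves out clinical progression, which censors some progressors informatively

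*Combined protocol and SAP*

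**What the plan says.** **PFS.** Section 11.2 lists three kinds of event: radiographic progression by RECIST 1.1 (including relapse from CR), clinical progression documented by the treating provider, and death from any cause. Section 13.2 repeats the clinical component in its PFS paragraph: "Disease progression will be assessed using RECIST (version 1.1) and/or documented clinical progression as assessed by the treating provider".

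**TTP.** Section 11.3 runs TTP from first dose to "the date of documented disease progression (PD or relapse from CR as assessed using RECIST 1.1 criteria"), with no clinical component. It then compares the two endpoints: "It differs from PFS in that it does not include death in the definition of an event". Its censoring rule is "TTP will be censored at the date of the last scan for subjects without documentation of disease progression at the time of analysis".

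**Analysis plan.** Section 13.2 adds no TTP rule and only points back: "DOR and TTP were defined in second 11.3" (evidently meaning Section 11.3).

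**Imaging after treatment stops.**
- Section 10, footnotes 13 and 20, schedules an end-of-treatment CT 28 days (± 4 weeks) after the last dose. It need not be repeated if the visit is early and a scan exists from the past 6 weeks.
- Sections 1.4 and 5.12.2 continue imaging every two months until new therapy, progression, death, withdrawal or study closure.
- Section 5.12.3 moves patients who are off treatment with progression to survival follow-up. It does not say whether clinical progression alone counts.
- Appendix B asks sites to try to document objective progression after a patient stops for symptomatic deterioration.

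**The concern.** Taking death out of the PFS definition leaves RECIST progression plus clinical progression. The TTP definition leaves RECIST progression alone. The sentence comparing the two does not account for that gap, so two analysts could code the same patient differently.

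Followed literally, the definition treats a patient with clinical progression and no RECIST progression as still progression-free at the last scan. If there is no post-baseline scan, the last scan is the screening scan, at or before first dose, and the patient contributes no TTP follow-up. Leaving the risk set because of deterioration is not independent of progression, so Kaplan-Meier TTP is pushed upward.

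The situation is foreseeable here. Sections 11.2, 13.1 and 13.2 each provide for patients who discontinue for clinical progression before any post-baseline assessment. The first on-study scan is at week 8, or 56/30.4375 = 1.84 months, while the pancreatic cancer trial cited in Section 13.1 had a median PFS of 1.5 months. A gap between reported TTP and PFS would naturally be read as deaths without progression, when part of it could come from the definition.

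**Working it through.** **Plan's own figure.** The documents give no TTP estimate, target or event count, so there is nothing to reproduce. The contradiction rests on the definitions.

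| Event | PFS (11.2, 13.2) | TTP (11.3) | Difference named in 11.3? |
|---|---|---|---|
| RECIST 1.1 PD or relapse from CR | event | event | – |
| Clinical progression | event | not an event | no |
| Death | event | not an event | yes |

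**Inputs for the size.**
- Scan interval w = 8 weeks (Section 10, footnote 13), or 1.84 months.
- Median time to progression m = 1.5 months (the trial cited in Section 13.1) or 2.3 months. The second is the exponential median that gives 30% progression-free at 4 months, the design alternative: 4 × ln 2 / ln(1/0.30) = 2.30.
- Assumptions, not in the documents: exponential progression times; no deaths; a share f of progressions declared clinically, f = 10%, 20% or 30%; a share g of those later documented as RECIST PD at the next scheduled scan, g = 0, 0.5 or 1.

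**Formula.** Let S = 2^(−w/m) be the probability of no progression over one scan interval, p = 1 − S, and h = f(1 − g) the share of progressions that never become RECIST PD. In each interval a proportion hp of those still progression-free is censored at the previous scan and (1 − h)p becomes an event at the next scan. The Kaplan-Meier factor per interval is 1 − (1 − h)p/(1 − hp) = S/(1 − hp). So at week 16:
- TTP as written = [S/(1 − hp)]²
- TTP counting clinical progression (equal to PFS when there are no deaths) = S²

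**Numbers.**
- m = 1.5: S = 2^(−1.84/1.5) = 0.427, p = 0.573, S² = 18.3%.
- m = 2.3: S = 2^(−1.84/2.3) = 0.574, p = 0.426, S² = 33.0%.
- Example, m = 1.5, f = 20%, g = 0: h = 0.20; 0.427/(1 − 0.20 × 0.573) = 0.483; squared = 23.3%; excess 5.0 points.

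Week-16 TTP as written, with the excess over S² in percentage points:

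| m (S²) | f | g = 0 | g = 0.5 | g = 1 |
|---|---|---|---|---|
| 1.5 mo (18.3%) | 10% | 20.5% (+2.3) | 19.4% (+1.1) | 18.3% (0) |
| | 20% | 23.3% (+5.0) | 20.5% (+2.3) | 18.3% (0) |
| | 30% | 26.6% (+8.4) | 21.9% (+3.6) | 18.3% (0) |
| 2.3 mo (33.0%) | 10% | 36.0% (+3.0) | 34.4% (+1.5) | 33.0% (0) |
| | 20% | 39.4% (+6.4) | 36.0% (+3.0) | 33.0% (0) |
| | 30% | 43.4% (+10.4) | 37.6% (+4.7) | 33.0% (0) |

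Simulation with 200,000 or more patients per setting agrees with these values to within sampling error.

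**Between scans.** Even with g = 1 the RECIST date falls after the clinical date. At 4 months, shortly after the week-16 scan, simulation with m = 1.5 and f = 20% gives 18.1% for TTP as written against 17.6% when clinical progression counts.

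**Median.** With m = 1.5, f = 30% and g = 0, the week-8 estimate is 0.427/(1 − 0.30 × 0.573) = 51.6%. It stays above 50%, so the reported median moves from the first scan (1.84 months) to the second (3.68 months). With g = 0.5 it stays at 1.84.

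**The case against.** The strongest reply is the later imaging. A reader might infer that every patient stopped for clinical progression is censored at the scan before the deterioration. The documents do not support that: the end-of-treatment CT, the two-monthly imaging and the Appendix B instruction can all turn a clinical progression into a RECIST event, only at a later date. This reply stands in part, and it is why the range starts at about zero. It does not remove the problem. The end-of-treatment scan can be waived, imaging stops at new therapy, progression or death, and Section 5.12.3 leaves open whether clinical progression ends imaging.

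A second reply is that RECIST-only TTP is a coherent choice, since Appendix B itself separates symptomatic deterioration from objective progression. That also stands. A reader might infer from the comparison with PFS that the omission was accidental, but the text does not show intent, and it does not say that death is the sole difference; it names no other. RECIST-only TTP would still need both differences stated, and the informative censoring would remain.

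A third reply is that the effect is small against the noise. With 21 evaluable patients, the standard error of a proportion of 18% to 33% is √(0.18 × 0.82/21) = 8.4 to √(0.33 × 0.67/21) = 10.3 points, a 95% half-width of 16 to 20 points. That is correct and supports a low priority. But the bias has a known direction, and confidence intervals do not reflect it.

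**Conclusion.** The point holds as a minor inconsistency in an exploratory endpoint. TTP differs from PFS in two event components and Section 11.3 names one. The omitted component leads to informative censoring or late dating, and the direction is upward.

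The week-16 overstatement is about 0 to 10 percentage points: 2 to 10 if no clinical progressor later has documented RECIST PD, 1 to 5 if half do, about 0 if all do. This rests on the assumed 10% to 30% share of clinical progressions, exponential times with medians of 1.5 or 2.3 months, and no deaths. A larger share would give a larger bias. The 2-to-10 range alone should not be read as the estimate, because it assumes that none of the later scans ever documents progression.

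The primary DCR test, the sample size and PFS are unaffected. A reader might extend the point to duration of response, but Section 11.3 ends DOR at disease progression without the RECIST-only parenthesis, so the same contradiction is not shown there.

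**What to change.** In Section 11.3, define the TTP event as RECIST 1.1 PD, relapse from CR, or clinical progression documented by the treating provider, as for PFS. Keep censoring at the last scan for deaths without progression and for other patients without progression. Death is then the only difference in events, and the comparison sentence becomes complete.

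If RECIST-only TTP is intended, correct the sentence to state both differences and add a sensitivity analysis that counts clinical progression as an event on its documented date.

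Either route is a small wording change and needs no new data, because PFS already requires the clinical progression date. The first shortens reported TTP slightly; the second adds one descriptive analysis.

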12. DATA REPORTING / REGULATORY REQUIREMENTS

AE guidelines and instructions for AE reporting can be found in **Section 7.0 (Adverse Events: List and Reporting Requirements)**.

[name] will be holding the IND for this study. She will comply with all regulated reporting requirements to the FDA, local regulations, including ICH E6 guidelines for Good Clinical Practices.

12.1 Data Collection and Processing

All information will be collected on study-specific CRFs by study staff. These data will be reviewed for completeness and accuracy by the Principal Investigator at each site.

CRFs will be used to capture study results and data. The study coordinator or other authorized

study personnel will transcribe data from source documents onto eCRFs. Before or between visits, the IND Sponsor, or designee may request copies of the CRFs for preliminary medical review. Once the CRFs are complete and source-verified, the investigator must sign and date all required pages, verifying the accuracy of all data contained within the CRF.

Protocol Chair

The Protocol Chair and/or designee is responsible for performing the following tasks:

- Coordinating, developing, submitting, and obtaining approval for the protocol as well as its subsequent amendments.
- Assuring that all participating institutions are using the correct version of the protocol.
- Taking responsibility for the overall conduct of the study at all participating institutions and for monitoring the progress of the study.
- Reviewing and ensuring reporting of SAE
- Reviewing data from all sites.

Coordinating Center (Johns Hopkins University)

The Coordinating Center (or its representative) is responsible for performing the following tasks:

- Ensuring that IRB approval has been obtained at each participating site prior to the first subject registration at that site, and maintaining copies of IRB approvals from each site.
- Monitoring subject registration.
- Collecting and compiling data from each site.
- Establishing procedures for documentation, reporting, and submitting of AE's and SAE's to the Protocol Chair, and all applicable parties.
- Facilitating audits by securing selected source documents and research records from participating sites for audit, or by auditing at participating sites.

Participating Sites

Participating sites are responsible for performing the following tasks:

- Following the protocol as written, and the guidelines of Good Clinical Practice (GCP).
- Submitting data to the Coordinating Center.
- Consent subjects promptly.
- Providing sufficient experienced clinical and administrative staff and adequate facilities and equipment to conduct a collaborative trial according to the protocol.
- Maintaining regulatory binders on site and providing copies of all required documents to the Coordinating Center.

Collecting and submitting data according to the schedule specified by the protocol.

12.2 Safety Meetings

Scheduled meetings will take place weekly (or as needed based on enrollment) and will include the protocol principal investigator, study coordinator(s), research nurse(s), sub-investigators (as appropriate), collaborators (as appropriate), and biostatisticians (as appropriate) involved with the conduct of the protocol. During these meetings, matters related to the following will be discussed: safety of protocol participants, validity and integrity of the data, enrollment rate relative to expectation, characteristics of participants, retention of participants, adherence to protocol (potential or real protocol violations), data completeness, and progress of data for objectives.

Monthly teleconferences will be scheduled (or as needed based on enrollment) to include the Coordinating Center and the clinical trial site(s). During these meetings, the Coordinating Center and clinical trial sites shall discuss the following: study protocol updates, safety data, enrollment status, and progress of data for objectives.

12.3 Monitoring

This is a medium risk study under the Johns Hopkins Sidney Kimmel Comprehensive Cancer Center (SKCCC) Data Safety Monitoring Plan (DSMP, 2/21/2019). Data monitoring of this protocol will occur on a regular basis with the frequency dependent on the rate of subject accrual and the progress of the study. Eligibility for all sites will be monitored by the Protocol Chair. The IND Sponsor and PI at each site shall internally monitor the progress of the trial, including review and confirmation of all safety/treatment-related outcomes, response assessments, safety reports and/or any related source documentation. Additional data and safety monitoring oversight will also be performed by the SKCCC Safety Monitoring Committee (SMC - as defined in the DSMP). External monitoring will occur according to the following guidelines:

Johns Hopkins SKCCC: The protocol will be monitored externally by the SKCCC CRO in accordance with SKCCC guidelines. Trial monitoring and reporting will be done through the Safety Monitoring Committee (SMC) at SKCCC.

Participating site(s): The protocol will be monitored by authorized representatives of the coordinating center. A report of the reviews will be submitted to the IND Sponsor and the SKCCC CRO.

Authorized representatives of the Coordinating Center may visit the satellite site(s) to perform audits or inspections, including source data verification. The purpose of these audits or inspections is to systematically and independently examine all trial-related activities and documents to determine whether these activities were conducted and data were recorded, analyzed, and accurately reported according to the protocol, Good Clinical Practice (GCP), and any applicable regulatory requirements.

12.4 Study Documentation

12.4.1 Informed Consent and Authorization for use and Disclosure of Protected Health Information

Written informed consent and authorization of use and disclosure of protected health information (PHI) must be obtained from each subject (or the subject's legally authorized representative) before performing any study-specific screening/baseline period evaluations. The ICF and authorization for use and disclosure of PHI, which is prepared by the investigator or the site, must be reviewed and approved by the IND Sponsor, the study monitor (if applicable), and the site's IRB before the initiation of the study.

12.4.2 Investigator Study Files

The IND Sponsor or designee will be responsible for maintaining original and backup of all CRF data. Investigator will maintain backup of all electronic data systems used for primary documentation or source documentation. Backup of electronic data will be performed periodically. Backup records will be stored at a secure location on site and backup and recovery logs will be maintained to facilitate data recovery.

Changes to any electronic records require an audit trail, in accordance with 21 CFR 11.10(e), and should include who made the changes and when and why the changes were made. An audit trail is defined as a secure, computer-generated, time-stamped electronic record that will allow reconstruction of the course of events relating to the creation, modification and deletion of an electronic record. Audit trails must be created incrementally, in chronological order and in a manner that does not allow new audit trail information to overwrite existing data. Audit trails should be in a readable format and readily available at the study site and any other location where electronic study records are maintained.

Audit trails are generated automatically for eCRFs. The investigator is responsible for maintaining audit trails of all electronic data systems used for primary documentation or source documentation.

